## 3) Background

Family-centered rounds (**FCR**) are multidisciplinary bedside rounds for hospitalized patients with active engagement by the family. FCR provides many benefits to patients, families, and providers, including fewer harmful errors, shortened hospital stays, reduced parental anxiety, improved family experience, and enhanced staff teamwork. For these reasons, FCR is recognized as a best practice for hospitalized children. However, because active family engagement is required, FCR has only been possible for patients whose families can physically be at the bedside during hospital rounds.

In the neonatal intensive care unit (**NICU**), barriers exist that limit family presence at the bedside. Critically ill neonates may be hospitalized for extended

**PROTOCOL TITLE: Virtual Family-Centered Rounds in the Neonatal Intensive Care Unit:  
A Randomized Clinical Trial**

periods of time. Their parents or guardians (“parents” hereafter) often live far from the hospital and have travel, financial, work, or childcare constraints that limit their ability to be physically present in the NICU. These barriers are particularly challenging for rural and low-income parents. NICU parents have high rates of depression, anxiety, and post-traumatic stress, and reduced visitation with their infant can exacerbate their depression and inhibit parental-newborn attachment. These parental factors impact the neonate, too. Early attachment impacts intelligence and emotional wellbeing later in life. Parental psychological support and engagement can shorten the NICU hospitalization and facilitate breast milk feeding. Breast milk fed infants have improved near-term (e.g., lower risk of sepsis and improved cognitive development) and long-term outcomes (e.g., lower risk of hypertension, diabetes, and obesity).

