**8) Data and/or Specimen Management and Confidentiality**

I understand that if this study involves the use of the UC Davis Health Electronic Health Record (EMR/EPIC) also contains the clinical data for Marshall Medical Center (MMC). I understand that MMC patient data cannot be accessed for research purposes and that I must take the necessary steps to ensure that MMC data is not accessed, used, or disclosed for UC Davis Health research purposes.

I understand that if this study involves use of UC Davis students' educational records (including records in the PI's own possession such as course exams/assignments), I must consult with the Registrar's office to see if all requirements of the Family Educational Rights and Privacy Act (FERPA) are satisfied.

**DATA ANALYSIS:** We will analyze subject data according to their assigned group (intervention vs. control). We will use descriptive statistics to summarize subject-level characteristics. We will compare neonatal and parental characteristics between study arms using Pearson's Chi-square test for categorical variables, t-test for normally distributed continuous variables, and nonparametric equality-of-medians test for non-normally distributed continuous variables. Generalized linear models will be used to estimate effect sizes and to test hypotheses for study outcomes, using a binary indicator for intervention assignment as the independent variable of interest and including a parsimonious set of demographic and clinical characteristics as covariates. We will analyze all available data and anticipate high data completion rates, based on our pilot trial. We will conduct sensitivity analyses using multiple imputation approaches for missing data to complement the primary analysis.

**SAMPLE SIZE:** We specified effect sizes of interest for all the trial outcomes and determined the necessary sample size to satisfy each. The sample size estimation that satisfies length of stay requirements also satisfies requirements for all other outcomes of interest, except for medical errors (which are rare and

**PROTOCOL TITLE: Virtual Family-Centered Rounds in the Neonatal Intensive Care Unit:  
A Randomized Clinical Trial**

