thus this outcome will be considered exploratory. Outcome distributional assumptions were based on data from our pilot trial or other relevant literature. Pilot trial baseline mean log transformed length of stay +/- standard deviation (SD) was 3.0 +/- 1.0 days. Minimally clinically important differences (MCID) were based on the literature when available or via consensus opinion elicited from NICU clinicians we consulted. For the length of stay outcome, experts specified that a 25% reduction in geometric mean length of stay was of interest. A randomized sample of 447 neonates (298 intervention, 149 control) subject to 4% attrition in each arm yields a sufficient sample size (429 neonates) to provide 80% power (under two-sided testing, alpha=5%) to detect this MCID. This estimated attrition is based on 4 of 110 randomized subjects in the pilot trial being excluded from final analysis (e.g., child protective visitation restrictions placed after randomization). Parent-reported outcomes assume a survey response rate of 75% (thus n=321 parents). Note: Regarding sample size for the interviews, we anticipate interviewing ~15 parents, ~10 nurses, and ~10 physicians. Consistent with standard qualitative methods, we will continue to sample interview participants until we reach thematic saturation, thus we cannot specify a priori the exact number of interviewees.

All virtual FCR encounters will occur using an application platform that is approved by Information Technology at UC Davis Health System as meeting HIPAA and HITECH data security requirements. The only telehealth communication that will occur will be through the HIPAA-compliant application. No telehealth encounter will be recorded or stored in any way.

Participants will decide to what extent they want to participate in the interviews and surveys. There will be no personal or intrusive questions. In all steps of this pilot study, the risk of loss of confidentiality is very low given the measures described above to protect PHI.

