## STATISTICAL ANALYSIS PLAN

### Statistical methods for primary and secondary outcomes

Our primary analysis strategy will analyze all available data from participating family units and their members, with groups defined according to the randomized assignment (intervention versus control) for that family unit. We will use graphical and analytical descriptive statistics to summarize infant, parent, and family unit characteristics. We will use methods for clustered survey data to adjust confidence intervals for family units with multiple parental respondents. We will not use cluster-adjusted confidence intervals for family units with multiple infants unless the mean number of infants per family unit unexpectedly exceeds 1.10.

We will use generalized linear models to estimate intervention effect sizes and confidence intervals and to test hypotheses for outcomes. Independent variables will include a binary indicator for intervention assignment along with a parsimonious set of subject characteristics as covariates (parent age, race, ethnicity, gender, education, transportation security, marital status, other children dependents, digital literacy score). We will specify the generalized linear mixed models as linear, logistic, or Poisson regressions, according to the outcome type. Random effects will be specified to accommodate the multilevel structure of the data and the nesting of longitudinal measurements, when applicable, within parents and the nesting of parents and infants within family units.

To account for increased exposure among subjects with longer neonatal intensive care unit (NICU) stays when analyzing the primary outcome, we will use Poisson regression to compare rates for the family-centered rounds (FCR) parent attendance outcome between intervention vs. control group subjects, using the numerator for this outcome as the dependent variable and using the logarithm of the denominator as an offset term. We will also use Poisson

regression for analyzing the error rate outcomes, with the offset being the logarithm of the number of days in the NICU. The exponentiation of the Poisson regression coefficient for the treatment indicator will thus represent an adjusted between-arm rate ratio for FCR parent attendance.

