### **Methods for additional analyses (e.g. subgroup analyses)**

We will conduct mediation analysis to evaluate relationships between parent activation and the other secondary and exploratory outcomes. We will also evaluate relationships between FCR attendance and the other outcomes. For example, the intervention effect on HRQOL may be mediated by FCR attendance with a dose-response relationship. Thus, if we find a positive intervention effect on HRQOL, we will explore FCR attendance mediation using similar methods. We anticipate that the intervention effect on the following outcomes will be mediated by FCR attendance with a dose-response relationship: parent experience, family-centered care, parent activation, parent HRQOL, length of stay, and breastmilk feeding.

We will explore heterogeneity of the treatment effects, using rigorous analyses based on including interaction terms for the candidate effect modifier and the intervention effect term(s).

Candidate effect modifiers will include residence-to-NICU distance, neighborhood health conditions, parent race and ethnicity, parent transportation security, other children dependents, parent computer/smart device access, parent internet access, and parent digital literacy score. For these terms, each will be evaluated without correction for multiple discovery. Other candidate effect modifiers will be evaluated as part of a comprehensive examination of intervention effects and for these, we will control the false discovery rate at 10%.

We will decompose the FCR parent attendance outcome measure by the type of attendance to separate the in-person and virtual components. We will explore the type of attendance as an outcome variable and as a predictor of the secondary outcomes. We will include a statistical exploration within the intervention arm for whether higher virtual FCR attendance is associated with differences in in-person FCR attendance. Additionally, we will fit regression models for each secondary outcome that simultaneously include measures of both virtual and in-person FCR attendance, allowing us to assess and compare whether the incremental benefits of higher FCR attendance are similar between both types of attendance.

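### The covariate list for the primary attendance model omits residence-to-NICU distance, which the SAP already plans to use as an effect modifier; pre-specifying it would probably give a modest gain in precision

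*Combined protocol and SAP*

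**What the plan says.** The SAP section on statistical methods for primary and secondary outcomes gives one covariate list for the outcome models: "parent age, race, ethnicity, gender, education, transportation security, marital status, other children dependents, digital literacy score". It has nine items, is not worded as a set of examples, and has no distance term. For the primary outcome, "we will use Poisson regression to compare rates for the family-centered rounds (FCR) parent attendance outcome", with the log of the number of round encounters as offset. The same section says that "Random effects will be specified to accommodate the multilevel structure of the data", where applicable. It does not say whether that covers the attendance model.

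The SAP section on additional analyses puts distance first among the effect modifiers: "Candidate effect modifiers will include residence-to-NICU distance, neighborhood health conditions, parent race and ethnicity, parent transportation security". Protocol section 3 (Background) says parents "often live far from the hospital and have travel, financial, work, or childcare constraints" that limit their presence in the NICU. Distance is one barrier among several there, and the barriers are not ranked.

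Protocol section 8 describes the models as "including a parsimonious set of demographic and clinical characteristics as covariates" and does not itemise the set. Neither document gives a reason for leaving distance out beyond parsimony.

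**The concern.** Home-to-hospital distance is settled before randomisation, bears directly on whether a parent can attend in person, and is part of the rationale for offering rounds by video. A baseline variable of that kind is a natural covariate for an attendance outcome. If it predicts attendance beyond the nine listed items, leaving it out makes the estimated rate ratio more variable than it need be.

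Protocol section 7 describes a random allocation list at 2:1 and mentions no stratification. A chance difference in distance between the arms is therefore possible and would go unadjusted. Adding distance after such a difference had been seen would be open to challenge; adding it in advance would not. The distance-by-arm interaction model would also normally carry distance as a main effect, so the primary and interaction analyses would adjust for different variables.

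What is at stake is efficiency and pre-specification, not validity.

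**Working it through.** **1. The plan's own figure.** Protocol section 8 gives the SD of log length of stay as 1.0, a 25% reduction in geometric mean (|ln 0.75| = 0.2877), 2:1 allocation, 4% attrition, and a sample size chosen "to provide 80% power (under two-sided testing, alpha=5%) to detect this MCID".

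- Control arm: (1 + 1/2) × (1.960 + 0.842)² × 1.0² / 0.2877² = 142.3, so 143.
- Total: 3 × 143 = 429. Randomised: 429 / 0.96 = 446.9, so 447.

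The stated size reproduces, but it concerns length of stay. The documents give no attendance rate, effect size or variance, so it says nothing about precision for attendance.

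**2. Range of the gain.** Let R² be the share of between-infant variance in attendance that distance explains beyond the listed covariates. This is an assumption, as the documents give no value. The SE ratio is √(1 − R²) and the equivalent sample size is 429 / (1 − R²). For a notional test with 80% power without distance, power becomes Φ(2.802 / √(1 − R²) − 1.960).

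| Assumed R² | SE ratio | Equivalent N | Power |
|---|---|---|---|
| 1% | 0.995 | 433 | 80.4% |
| 5% | 0.975 | 452 | 82.0% |
| 10% | 0.949 | 477 | 84.0% |
| 20% | 0.894 | 536 | 87.9% |
| 30% | 0.837 | 613 | 91.8% |

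**3. Check in the offset Poisson model.** Simulation with 429 infants (286 and 143) and 400 replicates. Assumed: control attendance about 0.35 before between-infant variation, rate ratio 1.3, between-infant SD 0.6 on the log scale. Weekday rounds were drawn from the pilot length of stay. Each column gives the SE with distance divided by the SE without it.

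| Share explained | Empirical | Robust | Model-based Poisson |
|---|---|---|---|
| 0% | 0.996 | 0.990 | 1.003 |
| 5% | 0.978 | 0.966 | 1.003 |
| 10% | 0.950 | 0.951 | 1.003 |
| 20% | 0.929 | 0.902 | 1.003 |
| 30% | 0.859 | 0.856 | 1.004 |

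The empirical and robust columns follow the formula within simulation error. The model-based column does not move. That SE (0.035) was about one third of the true one (0.10), so its interval would be too narrow with or without distance.

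**4. With a random intercept.** In a random-intercept Poisson model (100 replicates, control attendance about 0.3, other assumptions as in step 3), adding distance changed the reported SE by factors of about 1.00, 0.96, 0.94 and 0.92 at 5%, 10%, 20% and 30%. The gain reaches the printed interval, but it is modest.

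**5. If virtual rounds weaken the link.** Beta-binomial simulation, 286 against 143, 1,500 replicates, none of the nine covariates in the model. R² refers to the control arm.

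| Control-arm R² | Slope in the intervention arm | SE ratio |
|---|---|---|
| 0.10 | equal | 0.93 |
| 0.10 | halved | 0.97 |
| 0.10 | zero | 0.98 |
| 0.24 | halved | 0.89 |
| 0.24 | zero | 0.95 |

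**6. Chance imbalance.** The standardised difference in mean distance has SE √(1/286 + 1/143) = 0.102. A difference of at least 0.2 SD in either direction has z = 0.2 / 0.102 = 1.95, so it arises in about 5% of trials.

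**The case against.** The strongest reply is that this is a preference, not an error. The SAP pre-specifies nine covariates and calls the set parsimonious. Two of them, transportation security and other dependent children, already cover part of the access barrier. Randomisation protects against bias, and a valid interval already allows for chance imbalance. Protocol section 8 states that the length-of-stay sample size suffices for every other outcome except medical errors. A distance-adjusted analysis will in effect exist through the planned interaction model, though only as an exploratory one. All of this stands. It limits the size and status of the point, but it gives no reason to leave out a variable the trial plans to have.

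A second reply is that distance does not shorten the interval from a plain Poisson model. That is correct (step 3), but only because that interval ignores the variation between infants. The reply therefore adds a condition to the fix and does not remove the case for it.

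Stronger readings that a reader might infer, and that the documents do not support:

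- *Distance is the main barrier, or the best predictor of attendance.* The background lists it unranked among other constraints.
- *The gain is worth 17% or 35% more neonates.* A simulation gives variance gains of that size at R² of 0.10 and 0.24 (SD ratios 0.924 and 0.862). It assumes one distance slope for both arms and leaves out all nine listed covariates. Step 5 shows smaller gains once the slopes differ, before any overlap with transportation security.
- *Distance is in hand for every neonate from the admission address.* Neither the data-collection list in protocol section 7 nor the participant-log fields in section 18 name an address or a distance. The SAP shows only that distance is planned for use.

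**Conclusion.** The point holds as an efficiency improvement. The pre-specified covariates omit a pre-randomisation variable that the SAP will use elsewhere and that the protocol ties to parental presence. Including it would probably sharpen the attendance rate ratio modestly and would adjust for chance imbalance in distance.

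For an assumed 1% to 30% of between-infant variance explained beyond the listed covariates, the true standard error falls by about 0.5% to 16%. The fall is smaller if virtual rounds loosen the link in the intervention arm, which is the trial's own premise. The lower end is negligible, and the documents do not show where in the range this trial lies.

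A reader might infer that the primary estimate is biased or that power for attendance is in danger. Neither follows: randomisation excludes the first, and nothing in the documents indicates the second.

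**What to change.** - Add baseline log residence-to-NICU distance to the pre-specified covariates of the primary attendance model and of the in-person and virtual attendance models.
- Name its source in the data-collection section, since none is given now.
- State how variation between infants enters the attendance standard errors: an infant-level random effect, or robust or quasi-Poisson standard errors. Say whether the SAP's random-effects sentence applies to this model. Without this step the gain would not appear in a valid interval.

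The cost is one degree of freedom per model and a slightly less parsimonious covariate set. No new variable is needed beyond the one the interaction analysis already requires, provided its source is confirmed.

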#### **4) Inclusion and Exclusion Criteria**

This study is a randomized trial to compare virtual family-centered rounds (**FCR**) to standard FCR for neonatal intensive care unit (**NICU**) patients. We will simultaneously conduct an intervention evaluation of this virtual FCR intervention. The unit of randomization is at the subject level (the neonate). The site is the UC Davis NICU. To gather necessary data on efficacy outcomes and on the 5 dimensions for the intervention evaluation (Reach, Effectiveness, Adoption, Implementation, Maintenance), survey data will be collected from the subjects’ parent or guardian (referred to as “parent” hereafter), electronic health record (EHR) data will be collected from UC Davis, and daily weekday FCR observations will be performed. To gather necessary data for the intervention evaluation, qualitative interviews will be performed.

- INCLUSION: (NEONATES) Neonates aged <365 days admitted to UC Davis neonatal intensive care unit (NICU) during the study period who have one or more parent or guardian that self-reports their preferred language to be English. This parent must also be non-incarcerated and aged  $\geq 18$  years.
- EXCLUSION: (NEONATES) Age > or = 365 days. Neonates with visitation or information restrictions placed by child protective services. Neonates with more than one admission during the trial period will be included only on their first admission.
- INCLUSION: (QUALITATIVE INTERVIEWS) Parents/guardians of the eligible patients (described above) and NICU clinicians (e.g., nurses, physicians). Age 18 years and older.
- EXCLUSION: (QUALITATIVE INTERVIEWS) Age less than 18 years. Non-English speaking.
- INCLUSION: (SURVEY) Parents/guardians of the eligible patients (described above). Age 18 years and older.

**PROTOCOL TITLE: Virtual Family-Centered Rounds in the Neonatal Intensive Care Unit:  
A Randomized Clinical Trial**

- EXCLUSION: (SURVEY) Age less than 18 years. Non-English speaking.

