#### **Methods in analysis to handle protocol non-adherence and any statistical methods to handle missing data**

The primary analysis strategy – a modified intention-to-treat analysis – differs from intention-to-treat only in that it will not require replacing missing data with imputed values. This ‘complete-case’ analysis strategy assumes that missingness is at random. Sensitivity analysis using multiple imputation will be performed to assess the potential impacts of nonignorable missingness and alternative approaches for handling infants whose disposition is not to the home

and thus for whom the outcome may not be as applicable. In particular, for the few infants who transfer to another unit or hospital, the parent-reported outcomes and the 30-day revisit/readmission outcomes are of limited applicability. Our modified intention-to-treat analysis will include these subjects, but alternative analysis that excludes such outcomes from infants not discharged to home would be warranted. We will also estimate alternative treatment effects, such as per-protocol and as-treated.

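### Nine parent covariates plus a complete-case primary analysis, with no rule for missing covariates, can drop neonates whose attendance and length of stay are observed

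*Combined protocol and SAP*

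**What the plan says.** The SAP section on statistical methods for primary and secondary outcomes uses generalized linear models to estimate effects and test hypotheses. The models contain the arm indicator and nine parent characteristics: age, race, ethnicity, gender, education, and then "transportation security, marital status, other children dependents, digital literacy score". No outcome is exempted. For the primary outcome, the exponentiated Poisson coefficient "will thus represent an adjusted between-arm rate ratio for FCR parent attendance". The same section opens with a broad aim: "Our primary analysis strategy will analyze all available data from participating family units and their members".

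The SAP section on non-adherence and missing data calls the primary analysis a modified intention-to-treat analysis that "differs from intention-to-treat only in that it will not require replacing missing data with imputed values", and labels it complete-case under missingness at random. Multiple imputation is secondary: "Sensitivity analysis using multiple imputation will be performed to assess the potential impacts of nonignorable missingness", and also to examine infants not discharged home. Protocol Section 8 (Data analysis) is more general: "We will conduct sensitivity analyses using multiple imputation approaches for missing data to complement the primary analysis". It also says that the team will "anticipate high data completion rates, based on our pilot trial", without a figure and without mentioning covariates.

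Protocol Section 7 (Data collection) takes attendance from weekday rounding observations and length of stay from the EHR. Section 8 contrasts survey outcomes, which cover responders only, with observation- and record-based outcomes, which are meant to cover every subject.

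The documents do not say where or when the nine covariates are collected, or whose values enter a neonate-level model when there are two parents.

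**The concern.** A regression with no rule for a missing covariate omits the whole record. Here the record is a neonate with all of its observed round encounters, or with a known length of stay. Outcome data that need no parent response would then depend on the completeness of parent items. That runs against the SAP's aim of using all available data and against the intent in Section 8 that non-survey outcomes cover everyone.

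The first cost is precision. Length of stay sets the sample size, and the calculation has no slack for lost covariates: the 4% attrition comes from 4 of 110 pilot subjects excluded from the final analysis. With nine items, small gaps can accumulate.

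The second cost is conditional. Section 7 describes retrospective EHR access, and the contact with control-arm parents that it names there is an invitation to the surveys, the first of which falls around discharge. An item that is not in the EHR, perhaps digital literacy or transportation security, may therefore be measured by survey after randomization. If so, the primary analysis would select families on a post-randomization response. Adjusting for digital literacy measured after use of the platform could also distort the comparison.

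**Working it through.** **Inputs.** From Section 8 (Sample size): SD of log length of stay 1.0; 25% reduction in geometric mean; two-sided 5%; 2:1 allocation; 447 randomized, 4% attrition, 429 analysable. From the SAP: nine covariates. Assumed, because the documents give no figure: 1%, 2% or 5% missing per item, with loss in proportion in both arms.

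**Reproducing the plan's figure.** The log-scale difference is −ln(0.75) = 0.2877. Control n = (1.960 + 0.842)² × 1.5 / 0.2877² = 142.3, so 143 control and 286 intervention, total 429; 429/0.96 = 446.9, so 447. The stated figures reproduce. With SE = √(1/286 + 1/143) = 0.1024, noncentral-t power is 80.0%.

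**Neonates kept.** If the same neonates miss every item, n = 429 × (1 − q). If the nine items are missing independently, n = 429 × (1 − q)⁹. These are the two reference cases; partial overlap lies between them.

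| Missing per item (q) | Pattern | Kept (intervention:control) | Lost | SE | Power, no precision gain |
|---|---|---|---|---|---|
| 0% | – | 429 (286:143) | 0 | 0.1024 | 80.0% |
| 1% | same neonates | 425 (283:142) | 4 | 0.1028 | 79.7% |
| 1% | independent | 392 (261:131) | 37 | 0.1071 | 76.4% |
| 2% | same neonates | 420 (280:140) | 9 | 0.1035 | 79.2% |
| 2% | independent | 358 (239:119) | 71 | 0.1122 | 72.5% |
| 5% | same neonates | 408 (272:136) | 21 | 0.1050 | 78.0% |
| 5% | independent | 270 (180:90) | 159 | 0.1291 | 60.3% |

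**Precision from the covariates.** If they explain a share R² of the variance, SE is multiplied by √(1 − R²). The documents give no R². To restore 80%, R² must be about 1 − (0.1024/SE)²: about 0.085 at n = 392, 0.167 at n = 358 and 0.37 at n = 270. At an assumed R² = 0.10, power is 84.0% with all 429 and about 80.7% with 392. The planned 80% survives in that case, but about 3 points are given up that retaining every neonate could largely keep.

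**Survey-only illustration.** Suppose one item came solely from the discharge survey. At the 75% response assumed for parent-reported outcomes, 321 neonates remain (214:107), 108 are lost, SE = 0.1184 and power is 67.8% (72.4% at R² = 0.10). If every neonate had two invited parents responding independently and either would do, coverage would be 1 − 0.25² = 93.75%: 402 remain (268:134), 27 are lost and power is 77.4%. The documents establish neither case.

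**Attendance.** The plan gives no event rate, dispersion or effect size for the primary outcome, so the power lost there cannot be computed.

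**The case against.** The SAP never says that one missing item removes a neonate. It says that imputation is not required, and the examples that follow concern outcomes. A missing-value category, or the second parent's value, would be compatible with the text. This stands against the flat reading, which a reader might infer, that any single missing parent item excludes the infant. It does not supply a rule: the strategy is named complete-case and covariates are not exempted.

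Multiple imputation is already planned, and the wording in Section 8 is wide enough to include covariates. That is real mitigation. It leaves the primary estimate as it was, and the SAP's own list of purposes does not mention covariates.

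The larger losses need independent missingness, whereas items from one form or one parent tend to be missing together. With full overlap the cost is at most about 2 points of power. This stands, and so does the offset from precision.

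A reader might also infer that a quarter of neonates will be lost, because survey response is put at 75%. That rate is for parent-reported outcomes, each eligible parent is invited separately, and no covariate is stated to come from the survey. Some parent facts are evidently known at screening, since eligibility needs a parent aged at least 18 and "one or more parent or guardian that self-reports their preferred language to be English".

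Finally, complete-case regression gives a valid treatment coefficient when missingness is unrelated to the outcome given arm and covariates. A claim that the primary result will be biased is therefore not supported.

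**Conclusion.** The concern holds as a gap between two stated rules: covariate adjustment of the outcome models, and a complete-case primary analysis with no provision for missing covariates. Applied as written, they discard observed attendance and EHR outcomes for neonates whose modelled parent covariates are incomplete. The loss ranges from nothing, if all nine items are complete, to the values tabulated above for length of stay. Those values rest on assumed missingness rates, equal loss across arms and, in the table, no precision gain.

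Selection by survey response, and adjustment for a post-randomization digital literacy score, remain possibilities. The documents do not fix the source or timing of the covariates, so neither can be asserted or sized. The point should be fixed before analysis. Confidence is medium, because the practical size turns on data that the plan does not report.

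**What to change.** For outcomes taken from rounding observations or the EHR, state in the SAP that:

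- every randomized neonate with an observed outcome stays in the primary adjusted model;
- missing baseline covariates are multiply imputed;
- the complete-case fit is the sensitivity analysis.

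For each of the nine covariates, give its source, when it is measured relative to randomization, and which parent's value is used when there are two. Leave out of the primary model any covariate measured after randomization that the intervention could affect; digital literacy is the one to check first.

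Adjusting only for pre-randomization variables available for every neonate would also retain everyone, but it gives up some prespecified socioeconomic covariates and any precision they bring.

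The cost is SAP wording and slightly more analysis work. No extra participants or data are needed, and multiple imputation is already in the plan.
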